3.3.2 Total Number of Study Sites/Total Number of Subjects Projected

Study site: Neonatal/infant intensive care unit at the Children's Hospital of Philadelphia.

Up to 103 infants will be enrolled in the study to produce up to 52 evaluable subjects (phase 1 trial + observational cohort). These numbers are estimated according to the enrollment flow diagram shown in **Figure 7**. Up to 26 infants are expected to receive the study drug to produce up to 24 infants with evaluable trial data. These numbers for the phase 1 trial account for the 24 infants needed to enroll up to 6 infants per each of the 4 evaluated doses (assuming 1 infant with a toxic response per dose level) plus withdrawal of up to 2 infants (~10%) prior to receiving *14 drug doses* for reasons other than a toxic response. We will target a minimum of 12 infants in the observational cohort. Enrollment in the observational (non-treated) cohort will be capped at 28 infants.

[figure not shown]

Figure 7. Flow diagram of estimated maximum enrollment numbers

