^a "Day 0" procedures to be completed ≤7 days prior to administration of the first study drug dose. The quantitative tracheal aspirate culture and cell count differential obtained during the screening phase will be used for the laboratory values. Prior to initiating study drug therapy, one additional tracheal aspirate will be collected for cytokine level measurements and 16s sequencing.

^b "Day 15" procedures to be completed ≤48 hours after administration of the last study drug dose

° Follow-up tracheal aspirate for quantitative culture will be collected 14 days after the last administered dose of inhaled tobramycin or on the day of planned tracheal extubation if earlier

^d Tracheal aspirate for tobramycin level measurements obtained on trial day 7 will be collected approximately 1hr, 3hr, 6hr, 9hr, and 11hr after drug administration. Samples collected on trial days 4, 10, and 14 will be collected approximately 11hr after administration of doses number 8, 20 and 28, respectively.

e Serum and blood tobramycin trough levels will be drawn concurrently, 11 hours after administration of the previous dose

^f Blood draws for comprehensive metabolic panels should be bundled with draws for tobramycin trough levels or other clinically ordered blood draws. Comprehensive panel to include a magnesium and phosphorus level on day 7 and 14.

^g Serum and blood tobramycin peak levels will be drawn concurrently, 1 hour after completion of the previous dose

^h Up to 6 blood tobramycin levels per infant will be drawn concurrent with clinically ordered blood draws.

ⁱ Weekly medical record review to assess for adverse events will take place until hospital discharge

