4.7.1 Early Termination Procedures

Subjects who are removed from the phase 1 trial early will undergo measurement of at least 1 serum tobramycin trough, a comprehensive metabolic panel, and collection of 2 tracheal aspirate samples after administration of the final tobramycin dose – unless these procedures are refused by the parent or physician. Laboratory testing may be repeated at the discretion of the research and medical teams for safety purposes. Review of the medical record will also continue as appropriate unless refused by the parent or guardian.

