4.7.2 Addition of Trial Participants after Early Termination

Additional research subjects will be added to the phase 1 trial as per the 3+3 design (**Figure 8**). In addition, subjects who are removed early from the trial for reasons other than

a toxic response or safety concern related to the investigational drug will be replaced 1:1 if fewer than 14 *doses* of inhaled tobramycin were administered. Up to 2 subjects total and no more than 1 per dose level, who receive \geq 14 *doses* of inhaled tobramycin, are removed early from the trial for reasons other than a toxic response or safety concern related to the investigational drug, and do not meet criteria for any of the primary tolerability endpoints will inform progression through the 3+3 trial design *without requiring participant replacement*. This is supported by the available data which show that elevated serum tobramycin trough levels in infants and young children are typically observed within the first 7 days of inhalational administration during every 12-hour dosing.⁴⁸⁻⁵⁰ PK analyses in young children demonstrate similar serum tobramycin levels are obtained after 28 days and after 56 days of inhaled tobramycin use suggesting negligible serum drug accumulation or impaired renal function when initial levels are reassuring.²¹

At least 3 infants must receive the full 14-day treatment course (28 doses) of the dose that is ultimately defined as the maximum tolerated dose at the end of this trial. Participants will be added as needed to fulfill this requirement. If the 300mg dose level is completed in 3 participants and none show evidence of a toxic response, up to 3 additional infants will be enrolled to receive to receive 300mg. This will provide a more robust assessment of drug tolerability and PK. The trial will be stopped if 2 of the additional infants receiving 300mg (2 out of 5 or 2 out of 6) develop a toxic response. In that event, the 216mg dose will be considered the maximum tolerated identified in this study.

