5.2.4 Individual Subject Stopping Rules

A study subject will be removed from the phase 1 trial and will not receive additional doses of the study drug if he/she develops a toxic response defined as any of the following:

- Trough serum tobramycin level (measured 11 hours after the last administered dose) ≥1µg/mL
- Increase in serum creatinine level by ≥0.3mg/dL above the pre-trial level¹⁻³
- Increase in serum creatinine >1.5-fold above the pre-trial level¹⁻³
- Urine output <0.5mL/kg/hr for 12 hours¹⁻³
- Any other serious adverse event possibly attributable to the investigational drug

Subjects may also be withdrawn from the study for reasons that do not meet the above criteria as described in section 4.7.

If an infant commences the trial and the primary medical team subsequently chooses to prescribe a systemic antibiotic (e.g., for the positive tracheal aspirate or another suspected infection that was unknown/not present at the time of enrollment), the infant will stop the phase 1 trial early. No additional doses of inhaled tobramycin will be administered but final laboratory testing will be performed.

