5.3 Efficacy Evaluations

Measures of potential drug efficacy will be assessed as secondary, exploratory endpoints. These will include the following outcomes:

• Change (pre vs post treatment) in tracheal aspirate pathogenic bacterial colony forming unit (CFU) counts measured by high resolution culture

Tracheal aspirates for high resolution culture will be obtained \leq 7 days prior to initiating inhaled tobramycin (as part of the screening procedures), \leq 48 hours after completing the final drug dose, and 14 days after completing the final drug dose (or on the day of planned tracheal extubation if earlier) (see schedule under section 4.3). For infants enrolled in the observational (non-treated) cohort, tracheal aspirate for culture will be obtained \leq 7 days prior to initiating the 14-day observation period (as part of the screening procedures) and \leq 48 hours after completing the observation period. These tests will be performed in the CHOP clinical laboratory as described in section 5.1.3.

Reduction in number and eradication of pathogenic GNR bacteria from the airways is anticipated to result in clinical benefit. Evidence from preterm infants with BPD indicates the presence of these organisms in the airway is associated with worse clinical outcomes.^{10,11} Moreover, data from children with CF demonstrate that early treatment of *P. aeruginosa* infection of the respiratory tract leads to improved clinical outcomes.^{16,88,89} As such, change in quantitative tracheal aspirate culture results following treatment with inhaled tobramycin is anticipated to be a suitable surrogate marker to assess the likelihood of clinical benefit. For this phase 1 feasibility trial, we will evaluate the relative intra-patient change in bacterial CFU counts and assess the association between the longitudinal change in CFU count, airway cytokine levels, and the RSS.

• Tracheal aspirate tobramycin levels

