6.3.3 Exploratory Secondary Safety and Efficacy Analyses

The exploratory secondary safety and efficacy endpoints listed in section 6.2 will be analyzed as described in **Table 7** (next page). In brief, all study data will first be summarized using standard descriptive statistics as appropriate based on data type and distribution. Assessments of change over time for all longitudinal secondary outcome data will first be assessed graphically, with and without stratification by the administered tobramycin dose. Next, paired t-tests or Wilcoxon sign rank tests will be used to compare

pre-trial baseline values to those recorded at later time points. Non-paired tests will be used to compare data baseline and subsequent data points between the infants in the phase 1 trial and observational (non-treated) cohorts.

	Values available for:			
Study outcome	Phase 1 trial cohort	Observational cohort	Statistical approach	
Secondary safety endpoints	Yes	Yes, for some endpoints	 Rates of the secondary tolerability endpoints will be summarized for each dose level. Descriptive, narrative details of these endpoints will also be provided as appropriate. Data on the rates of endotracheal tube obstruction, unplanned tracheal extubation, and audiology testing results will be compared between the trial and observational cohorts. Planned comparisons of audiology testing results are described in the Protection of Human Subjects document. 	
Secondary efficacy endpoints				
Negative TA culture for the target GNR	Yes	No	 Primary exploratory efficacy endpoint. Rates will be summarized for the trial cohort as a whole and stratified by drug dose level. 	
Change in TA GNR pathogen CFU	Yes	No	 Absolute (pre vs post) and relative change ([post trial – pre trial] / pre trial) in the target organism CFU/mL on the log₁₀ scale will be calculated for each phase 1 trial participant. Paired t-tests or Wilcoxon sign rank tests as appropriate will be used to compare pre- vs. post-trial absolute CFU/mL values for the whole cohort and stratified by drug dose level. 	
Tracheal aspirate tobramycin levels	Yes	No	 Values, stratified by drug dose, will be compared to established concentrations necessary to overcome the minimum inhibitory concentration needed to kill 90% of detected bacterial isolates (MIC₉₀).^{90,91} Values will also be used in our PK analyses. 	

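### Table 7 takes no account of systemic antibiotics started before a post-treatment culture, so clearance caused by the antibiotic can be credited to inhaled tobramycin

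*Combined protocol and SAP*

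**What the plan says.** Section 5.2.4 stops the phase 1 trial for an infant whose team chooses to "prescribe a systemic antibiotic (e.g., for the positive tracheal aspirate or another suspected infection". No more study drug is given, but final laboratory testing goes ahead. For infants removed early, section 4.7.1 asks for "collection of 2 tracheal aspirate samples after administration of the final tobramycin dose", unless refused. It does not say when these are taken relative to the antibiotic.

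For trial infants generally, post-treatment samples are timed from the last dose given. The first is due within 48 hours. For the second, Table 5 note c states "Follow-up tracheal aspirate for quantitative culture will be collected 14 days after the last administered dose of inhaled tobramycin", or on the day of planned extubation if that comes earlier. Section 5.1.4.3 lists quantitative culture with sensitivities at both times.

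In Table 7 (section 6.3.3), negative culture for the target GNR is the primary exploratory efficacy endpoint: "Rates will be summarized for the trial cohort as a whole and stratified by drug dose level". The CFU row uses paired tests to "compare pre- vs. post-trial absolute CFU/mL values for the whole cohort and stratified by drug dose level". Neither row mentions antibiotics. Section 5.3 explains why these results matter: "change in quantitative tracheal aspirate culture results following treatment with inhaled tobramycin is anticipated to be a suitable surrogate marker" for judging the likelihood of clinical benefit.

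**The concern.** The protocol itself foresees a systemic antibiotic aimed at the organism that defines the efficacy endpoint. If that drug is active and is started before the culture, its own effect is toward a negative result and a lower CFU count. Followed as written, Table 7 reports that result as part of the response to inhaled tobramycin.

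The stake is the preliminary efficacy signal. Section 1.7 says these data are to inform possible phase 2 and phase 3 trials, and with three to six infants per dose a single result is visible in the rate. Dose escalation is not at stake, because it rests on the composite safety endpoint alone.

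**Working it through.** **Tracing the text**

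1. Can an infant have an antibiotic before the culture? Yes. 5.2.4 and 4.7 make antibiotic initiation a reason to stop, 5.2.4 keeps final testing, and 4.7.1 sets no order between antibiotic and aspirate.
2. Are the aspirates cultured? 4.7.1 does not use the word culture. The link comes from 4.4 (one sample of each follow-up pair goes to the clinical laboratory) and 5.1.4.3 (that laboratory runs the quantitative culture).
3. Does another provision handle it?
   - The 7-day antibiotic exclusion in 3.4.2 protects only the baseline.
   - Replacement in 4.7.2 governs 3+3 progression.
   - Covariate selection in 6.3.3 belongs to optional mixed models and does not reach a summarized rate or a paired test.
   - Antibiotic use is recorded (4.4, 4.5), but no analysis rule uses it.
   - The only analysis set defined is for safety (6.3.2).

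**Size**

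The plan states no figure to reproduce here. Its counts are consistent: "Up to 26 infants are expected to receive the study drug to produce up to 24 infants with evaluable trial data", that is 24 + 2 = 26.

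Inputs:
- n = 3 or 6 per dose level (3+3 design), and 24 evaluable (3.3.2).
- k = number of affected infants. Section 4.7.2 lets early non-toxic stops with at least 14 doses stay without replacement: "Up to 2 subjects total and no more than 1 per dose level". So k = 1 per level and k = 2 overall are ceilings for that group, reached only if every such stop was for an antibiotic.
- q = chance that the antibiotic alone turns an otherwise positive culture negative. This is an assumption, shown at 0.25, 0.5 and 1.

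Shift in the negative-culture rate = k × q / n:

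| k, n | q=0.25 | q=0.5 | q=1 |
|---|---|---|---|
| 1 of 3 | 8.3 | 16.7 | 33.3 |
| 1 of 6 | 4.2 | 8.3 | 16.7 |
| 2 of 24 | 2.1 | 4.2 | 8.3 |

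(percentage points)

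Illustration: suppose 40% of the other 22 infants clear and both antibiotic-exposed infants are culture negative. As found, the rate is (0.4 × 22 + 2)/24 = 45.0%. With those two counted as not cleared it is (0.4 × 22)/24 = 36.7%. The gap is 2/24 = 8.3 points.

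CFU: an assumed extra fall of 1 to 3 log10 in one infant moves the mean change by 0.33 to 1.00 (n=3) or 0.17 to 0.50 (n=6).

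Chance that at least one infant starts an antibiotic before the culture = 1 − (1 − f)^n. For assumed f of 5%, 10% or 15% this is 71%, 92% or 98% for n=24, and 26%, 47% or 62% for n=6. This is the chance of an exposure, not of a bias: it ignores q and whether the drug covers the organism.

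For scale, exact 95% intervals are 4–78% for 2/6, 12–88% for 3/6, and 29–71% for an illustrative 12/24. The shifts are smaller than sampling error at both levels.

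**The case against.** The strongest reply is that the endpoint is exploratory, descriptive and imprecise, and that Table 7 is silent on antibiotics and does not adopt a wrong rule. Several stronger readings that a reader might draw do fail.

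- *The plan decides to count antibiotic-cleared infants as successes.* It does not. Table 7 gives no timepoint and no efficacy analysis set, and does not say whether infants replaced after fewer than 14 doses stay in the rate. A scenario such as 4 affected of 26 assumes that they do, and that every early stop was for an antibiotic.
- *The reported rate is too high.* This is not established for stopped infants. They receive fewer inhaled doses, and one treated for the positive aspirate may be a non-responder.
- *There is no untreated comparison.* Section 2.2 plans a CFU comparison with the observational cohort, whose infants are cultured before and after (5.3) and whose antibiotics are recorded (4.5). But that comparison has no antibiotic rule either, antibiotics in untreated infants could bias it against tobramycin, and Table 7 lists no observational value for either culture row.
- *No on-treatment culture can exist.* Table 5 schedules quantitative cultures only on days 0, 15 and 28, but 6.2 mentions cultures during treatment and clinically ordered cultures may occur.
- *Every stopped infant has a 14-day culture.* This is an inference. The two aspirates in 4.7.1 could be one visit soon after the last dose, with short antibiotic exposure.

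What remains is that neither culture row separates antibiotic-exposed results from the rest. Wide intervals do not correct a misattribution.

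**Conclusion.** The concern holds, at minor severity. As written, Table 7 allows clearance or CFU reduction caused by an active systemic antibiotic to be credited to inhaled tobramycin. The ceilings are 17 points (n=6) or 33 points (n=3) for one infant in a dose level, and 8 points for two of 24. They require an antibiotic that covers the organism and an otherwise positive culture that it turns negative (q=1). Section 1.4 expects limited airway penetration, so the true shift may be well below them. The documents give neither q nor the rate of antibiotic starts. The withdrawal allowances in 3.3.2 and 4.7.2 cover all non-toxic reasons and do not estimate that rate. The finding concerns how the efficacy signal is attributed. It does not show a net overstatement, and safety conclusions and 3+3 progression are untouched.

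**What to change.** 1. In the negative-culture row of Table 7, report two rates for each post-treatment culture: (a) infants who started a systemic antibiotic before that culture counted as not cleared, and (b) the result as found. If an antibiotic never turns a negative culture positive, the two bracket the clearance from the inhaled doses actually received. Optionally, repeat (a) counting only antibiotics active against the target organism by the reported sensitivities.
2. In the CFU row, keep the paired test on all infants. Add a sensitivity analysis that sets aside cultures taken after a systemic antibiotic, and list those infants with drug and start date. The restricted analysis should not replace the main one: it selects on a post-treatment event and may drop non-responders.
3. In 4.7.1, state that the quantitative-culture aspirate is taken before the first systemic antibiotic dose when this does not delay treatment.

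Cost: wording in two table rows and one sentence, with no additional samples. Exact antibiotic start dates must be captured in follow-up, where 4.4 provides only weekly abstraction. A study-team member must be available when the antibiotic is about to start, because 4.3.2 requires in-person guidance for collection. The downside of (a) is that it understates clearance when the antibiotic was given for an unrelated infection, which is why (b) stands beside it.

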5.2.5 Study Stopping Rules

The study stopping rules will follow the 3+3 dose escalation design shown in **Figure 9**. The study will be stopped if more than 1 subject develops a drug-related toxic response (any of the safety endpoints listed under section 5.2.1) at a single dosage level. Further enrollment will be stopped, but data analysis for those enrolled will continue until completed.

[figure not shown]

Figure 9. 3+3 dose escalation design schematic. *MTD: maximum tolerated dose*

5.3 Efficacy Evaluations

Measures of potential drug efficacy will be assessed as secondary, exploratory endpoints. These will include the following outcomes:

• Change (pre vs post treatment) in tracheal aspirate pathogenic bacterial colony forming unit (CFU) counts measured by high resolution culture

Tracheal aspirates for high resolution culture will be obtained \leq 7 days prior to initiating inhaled tobramycin (as part of the screening procedures), \leq 48 hours after completing the final drug dose, and 14 days after completing the final drug dose (or on the day of planned tracheal extubation if earlier) (see schedule under section 4.3). For infants enrolled in the observational (non-treated) cohort, tracheal aspirate for culture will be obtained \leq 7 days prior to initiating the 14-day observation period (as part of the screening procedures) and \leq 48 hours after completing the observation period. These tests will be performed in the CHOP clinical laboratory as described in section 5.1.3.

Reduction in number and eradication of pathogenic GNR bacteria from the airways is anticipated to result in clinical benefit. Evidence from preterm infants with BPD indicates the presence of these organisms in the airway is associated with worse clinical outcomes.^{10,11} Moreover, data from children with CF demonstrate that early treatment of *P. aeruginosa* infection of the respiratory tract leads to improved clinical outcomes.^{16,88,89} As such, change in quantitative tracheal aspirate culture results following treatment with inhaled tobramycin is anticipated to be a suitable surrogate marker to assess the likelihood of clinical benefit. For this phase 1 feasibility trial, we will evaluate the relative intra-patient change in bacterial CFU counts and assess the association between the longitudinal change in CFU count, airway cytokine levels, and the RSS.

• Tracheal aspirate tobramycin levels

Tracheal aspirate samples used for the measurement of tobramycin levels will be collected at the following times: (1) a single tracheal aspirate will be collected on days 4, 10, and 14, 11-hours after completion of the 8th, 20th, and 28th doses respectively; and (2) 5 samples will be collected on trial day 7, approximately 1-hour, 3-hours, 6-hours, 9-hours, and 11-hours after completion of the 14th tobramycin dose (see section 4.3) Tracheal aspirate drug levels will be measured in the laboratory of the University of Florida College of Pharmacology (see section 5.1.3). Tracheal aspirate drug levels will be concentrations needed to overcome the minimum inhibitory concentration necessary to kill 90% of detected bacterial isolates (MIC₉₀).^{90,91} Longitudinal change in tracheal aspirate levels will be modeled as part of the PK analyses. Correction for serum urea levels will be performed.

- Longitudinal change in the following respiratory support measures during the 14-day study period:
 - Fraction of inspired oxygen (FiO₂)
 - Ventilator mean airway pressure (MAP)
 - Respiratory severity score (MAP x FiO₂)

FiO₂ and mean airway pressure (MAP) are established clinical measures of respiratory disease severity. They characterize the amount of respiratory support (supplemental oxygen and positive airway pressure) required to maintain cardiorespiratory stability in infants receiving invasive respiratory support. The respiratory severity score (RSS) is a

simplified severity score calculated as the MAP multiplied by the FiO₂. The RSS is used in place of the oxygenation index (OI) owing to the infrequent availability of data on the partial pressure of arterial oxygen (PaO₂) in hospitalized infants. The RSS correlates well with OI in infants receiving mechanical ventilation and is a useful predictor of poor respiratory outcomes in preterm infants.⁹²⁻⁹⁴ FiO₂ and MAP values (measured by the mechanical ventilator and reported on the ventilator graphical interface), are recorded at least hourly in the respiratory flow sheet in the electronic medical record (EPIC). These data will be used to calculate daily, time-weighted values for FiO₂, MAP, and RSS. Longitudinal change in these respiratory support measures during the 14-day study period will be compared (1) between infants who participate in the phase 1 trial and those enrolled in the observational (non-treated) cohort, and (2) among participants in the phase 1 trial, stratified by the administered dose of inhaled tobramycin.

Owing to the expected heterogeneity in lung disease and respiratory support requirements of the enrolled infants, a protocolized ventilator management algorithm will not be utilized during this study. However, routine practice in our unit is to wean FiO₂ in infants with BPD to maintain SpO₂ \geq 90%. Most infants with BPD who require invasive respiratory in our unit are supported using a time-cycled, pressure-limited, volume-guarantee mode of ventilation that delivers 8-10mL/kg of tidal volume at mandated rates of 15-25 breaths per minute. The Draeger V500 ventilator is used in all infants receiving acute care in the CHOP N/IICU who are prescribed intermittent mechanical ventilation. On this mode of support, the ventilator automatically adjusts the positive inspiratory pressure (PIP) – within set limits – to deliver the goal tidal volume. Change in the PIP along with any clinical adjustments in the positive end expiratory pressure (PEEP) will be the primary determinants of any observed changes in the delivered MAP. Only infants with an endotracheal tube leak ≤20% will be enrolled in this trial to avoid ventilator leak compensation and artificial inflation of the PIP levels.⁹⁵ Of note, the Draeger V500 ventilator calculates the endotracheal leak proportion during all modes of intermittent ventilation employed in our unit.

• Change (pre vs post) in tracheal aspirate cytokine levels, neutrophil/WBC ratio, and patterns in the airway microbiome:

Tracheal aspirates collected \leq 7 days prior to initiating inhaled tobramycin, \leq 48 hours after completing the final drug dose, and 14 days after completing the final drug dose will be analyzed. Patterns in the airway microbiome will be assessed using 16s sequencing performed in the laboratories of the CHOP/Penn Microbiome Program. The following cytokine levels will be measured in tracheal aspirate samples: IL 1 β , 6, 8, 17A/F, 18, 22, 23, TNF- α , MIF, IFN- γ . These analyses will be performed in CHOP Translational Core Laboratory. Tracheal aspirate cell counts will be obtained by the CHOP clinical laboratory. Changes in the observed patterns in the airway microbiome, neutrophil/WBC ratio, and tracheal aspirate cytokine levels (compared to the pretreatment baseline) will be assessed, stratified by the treatment dosage level (see section 6.3 for further details of the analytical plan). For this phase 1 feasibility trial, we will evaluate the relative, intra-patient change in these measures as the association between these measures and clinical benefit in the study population is uncertain.

- Longitudinal change in the following measures of respiratory mechanics during the 14day study period:
 - Dynamic compliance (mL/cm H₂O)
 - Peak expiratory flow (L/min),

- Airway resistance (cm H₂O/L/sec)
- Carbon dioxide elimination (mL/min).

The Respironics NM3 respiratory parameter monitor will be used to record these data for 4 hours periods at study entry, on study day 7, and \leq 48 hours after completing the 14-day study period. These data will provide important information on the potential effects of inhaled tobramycin on respiratory function.

- Longitudinal change in the following measures of hypoxemia (SpO₂<80%):
 - Intermittent hypoxemia (SpO₂<80% lasting for 10s-3min)
 - Prolonged hypoxemia (SpO₂<80% lasting for >1min)
 - Daily proportion of time with hypoxemia

Daily frequency of intermittent and prolonged hypoxemic events are established, realtime indicators of cardiorespiratory stability in BPD.⁹⁶ Cumulative burden of hypoxemia predicts the severity of childhood neurodevelopmental delay.⁹⁷ These data will be recorded continuously throughout the study using a research pulse oximeter that will be placed in addition to the clinical multiparameter monitor. Nursing and medical staff will be instructed to use the clinically placed monitor for all care decisions.

